11.1 Assessments

Outcome data will be recorded daily by the research nurse for all recruited participants (up to and including Day 28, or until discharge). Patient reported outcome data (health-related quality of life and resource use questionnaires) will be recorded at day 28 and day 90 (with the exception of those recruited within the last 3 months of the study).

Research nurses will review observation and medication charts, and medical notes for all recruited participants to collect the data described in Table 1 below:

Table 1: Outcome data collection

Outcome	Data Source	Type of data	Frequency	By Whom
Antibiotic (Abx) initiation	Observation (Obs) charts/medical notes/drug charts	Time of initiation, Abx type, dose, duration	Admission/Daily	Research Nurse
Abx use (IV and Oral) in-patient	Obs charts/medical notes/drug charts	Abx type, dose, duration	Daily	Research Nurse
Abx use (IV and Oral) post discharge up to 28 days	Obs charts/medical notes/drug charts/patient report/GP record	Abx type, dose, duration	At 28 day	Research Nurse
Adverse events	Obs charts/medical notes	Date, type	Daily	Research Nurse
ICU usage	Medical notes	Date, details of admission to ICU	Daily	Research Nurse
COVID diagnosis	Medical notes	Date, clinical or laboratory confirmed	At 28 day	Research Nurse
Unscheduled readmissions	Medical notes	ICU re-admissions, re-admissions post discharge	Daily	Research Nurse
Mortality	Medical notes	Date, Description	If before Day 28	Research Nurse
Discharge	Medical notes	Date, Description	If before Day 28	Research Nurse
Serious Adverse Drug Reactions (ADRs)	Medical notes	ADR(s)	Daily	Research Nurse
Health utility	Patient reported	-	Day 28 and Day 90	EQ-5D/5L, Patient reported questionnaire, collected by

				telephone or by post
Health-related Quality of Life (EQ-5D/5L)	Patient reported	-	Day 28 and Day 90	Patient reported, collected by telephone, or by post
Resource use	Patient reported	Direct medical costs and resource use	Day 28 and Day 90	Patient reported, collected by telephone, or by post

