18.2 Health Economics

Economic analyses of the project have been planned based on expected primary and secondary outcomes of health intervention. As per the primary research question of the project, we expect that in ED patients managed as suspected sepsis, the addition of PCT to the NEWS2 scoring measurement may lead to a reduction in antibiotic initiation with at least no increase in 28-day mortality compared to the NEWS2 scoring alone. The secondary research question considers a broader aspect of economic evaluation that includes the societal perspective including the preferences of patients and family members. So, it examines if the proposed intervention would be cost-effective from the societal perspective (including household consequences).

In economic analyses, we shall apply NHS and societal perspective to address the decision making in the health system and on the society respectively. They will follow the intention-to-treat of the primary clinical effectiveness and safety analyses. Missing economic data will be imputed in a standard manner. The costs borne by NHS and the patients will thus be considered in estimations wherever applicable.

- 1) Cost of illness per patient from sepsis in intervention arm (IA: PCT + NEWS2) and standard care arm (SCA: NEWS2 alone), from the NHS and patient household perspectives.
- 2) Cost-saved per unit investment into proposed IA due to avoided antibiotic prescription, reduction of hospitalizations, and other cost-savings
- 3) Cost-effectiveness analysis of proposed intervention (PCT + NEWS2) in comparison to standard care per life year saved and £ per QALY gained
- 4) Cost-benefit analysis of proposed intervention (PCT + NEWS2)

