18.2.1 Methods

1) Cost of illness

The cost of illness (COI) will be conducted using NHS perspective and patient's perspectives. Together these will constitute the societal perspective. It implies that data will be collected from two sources, i.e. the hospital and patients. Total costs of illness of sepsis care per patient from the ED to hospitalization will be estimated for the treatment of sepsis by multiplying the total incidences of sepsis with the unit cost of caring for a patient throughout an episode up to 28 days after discharge from hospital. In addition, the total cost of screening will be included, again both from health service and household perspective. Considering the need of care, 30 patients of each type (general ward and ICU), of 10 hospitals will be included to calculate the mean costs of illness, which will sum up a total of $30 \times 2 \times 10 = 600$ patients. Direct medical and non-medical as well as indirect costs (income loss) will be captured using a Standardbred questionnaire for patients and departmental- and patient-level costs from hospitals. By multiplying mean cost with incidence rates, the total costs will be estimated.

2) Cost saved per GBP invested in the proposed PCT intervention due to potentially avoided antibiotic prescription, avoided admissions, and other decreased resource use.

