Here, the net cost of intervention is to be compared with the cost saved on avoidable antibiotics to estimate the money saved per GBP invested in the intervention arm. The outcome data of the intervention in terms of antibiotic avoided will be collected from a comparison of the two arms. The difference in antibiotic prescribing (number of patients and dosages) for patients between IA and SCA will be recorded from the ED and hospital prescription records. The unit price of antibiotic per dose will be multiplied by the doses avoided. Together with the savings due to reduced hospital admissions this will capture the total costs of antibiotic avoided due to the proposed intervention. The costs of intervention will be captured by identifying and quantifying the inputs used for patients in IA and SCA, valuing the inputs into economic costs with necessary (if applicable) adjustments for time preferences [42]. Such costs of intervention from the existing UK study by Hex et al. [43] might be used if not available in the reporting hospitals. Incremental costs between IA and SCA will constitute the investment on the proposed intervention for comparing with costs saved due

to reduced antibiotic use. It should be noted here that this intervention cost will be used in the cost-effectiveness analysis (CEA) (point 3 below) and cost-benefit analysis (CBA) (point 4 below) for comparing with intervention outcomes.

3) Cost-effectiveness analysis of proposed intervention (PCT + NEWS2) in comparison with standard care.

i) Cost-effectiveness approach

Our CEA will be influenced by the assumption that the outcome on 28 day mortality of IA and SCA is non-inferior (no significant difference). It means that the CEA will in the first instance take the nature of a cost-consequence (minimization) analysis and only the costs of interventions (IA and SCA) need to be compared to find the cost-effective alternative [42, 44]. Here, sepsis care with lower costs (i.e. intervention costs), defined by cost per screened patient and cost per sepsis patient treated will be considered as the more cost-effective alternative.

ii) Cost-utility analysis

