Cost-Utility Analysis (CUA) of non-inferiority trials has been conducted elsewhere [45]. For decision making from the analysis, cost-effectiveness planes prove to be a valuable tool in the interpretation of the results in an economic equivalence or non-inferiority trial [45]. We consequently will conduct a CUA due to the expected non-inferiorly health outcomes between IA and SCA. Health outcomes (QALYs) between IA and SCA will be compared with incremental costs of intervention between the arms. To assess QALYs gained in each patient group, the EQ-5D-5L instrument will be used on each patient (or representative if the patient is not in a condition of responding) under investigation of this study at screening, the 28th day, and 90th day after randomization. All primary and secondary empirical outcomes will be compared against existing literature and systematic reviews [27, 46, 47] and other trial-based studies. If possible, a meta-analysis will be carried out. The different in costs of interventions in IA and SCA and change in health outcomes (QALYs gained) will be plotted in cost-effectiveness plane for interpreting the results of this non-inferiority trial [45].

iii) Decision-tree analysis

Using data on health outcome (QALYs) and economic outcome (Cost of intervention) and probability of correct diagnosis (including false positives and false negatives) by both procedure arms (IA and SCA) will be used for conducting probabilistic analyses based on a decision-tree using TreeAge Pros (TreeAge Company, Inc) and STATA in a probabilistic CEA. Here, patients are randomly drawn from the IA and SCA treatment arm datasets in a MonteCarlo procedure, until convergence to stable estimates. The patients may face adverse effects of treatment with antibiotics in both arms and consequently worse health status. Patients correctly treated may face different outcomes in terms of cure and health status change and related resources. All resource use, including those of complications will be related to specific costs of NHS services. Following the TreeAge pathways using transition probability distributions between health states, based on the in-trial findings and literature, costs and health utility (health status) we shall be able to estimate expected societal and health care costs and expected utility of the patients (expressed in QALYs placed in IA and SCA).

4) Cost-benefit analysis

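### The only stated window for patient-level costs runs to 28 days after discharge, so it varies with length of stay and does not match the day-28 and day-90 schedule for resource use and quality of life

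*Protocol*

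**What the plan says.** Section 18.2 lists the economic outputs. The first is a cost of illness per patient in the intervention arm and in the standard care arm, from the NHS and household perspectives. The third is a cost-effectiveness analysis of the intervention "in comparison to standard care per life year saved and £ per QALY gained".

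The methods in section 18.2.1 use more than one cost.

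- **Item 1), cost of illness.** Total cost is incidence multiplied by "the unit cost of caring for a patient throughout an episode up to 28 days after discharge from hospital". The costing sample is described as "30 patients of each type (general ward and ICU), of 10 hospitals will be included to calculate the mean costs of illness", 600 patients in all.
- **Item 2), cost saved per pound invested.** This item defines an intervention cost: "The costs of intervention will be captured by identifying and quantifying the inputs used for patients in IA and SCA". No end date is given. The text continues: "It should be noted here that this intervention cost will be used in the cost-effectiveness analysis (CEA) (point 3 below", and names the cost-benefit analysis as a second use.
- **Item 3 ii), cost-utility analysis.** EQ-5D-5L is taken "at screening, the 28th day, and 90th day after randomization". The comparison is worded as "Health outcomes (QALYs) between IA and SCA will be compared with incremental costs of intervention between the arms". No period is stated for those costs.

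Table 1 in section 11.1 schedules "Direct medical costs and resource use", reported by patients, at day 28 and day 90. Section 11.2 lists what those contacts cover, including admissions, medicines, GP and outpatient visits, and patients' own expenses. Patients recruited in the last three months are exempt from these questionnaires.

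**The concern.** Discharge happens after randomisation, and length of hospital stay is a secondary outcome (section 5.4). Section 18.2.1 treats fewer admissions (item 2) and fewer hospital days (item 4) as possible savings from the intervention. A cost window that closes a fixed time after discharge is therefore partly determined by the result being studied. If one arm goes home sooner, its patients are also followed for cost over a shorter calendar period. The hospital day saved is a real saving. The day that drops off the far end of the window is not: it is only no longer counted. A per-arm cost of illness built this way mixes the two.

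The window also does not line up with the data. Patient-reported resource use arrives at two fixed points after randomisation, and for most plausible stays the window closes between them. The protocol does not say that questionnaire items are dated so that they could be cut at a patient-specific day. Hospital records could be cut at any date. The household part of the cost is less easily separated.

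**Working it through.** **Inputs**

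- Cost window: 28 days after discharge (section 18.2.1, item 1).
- Resource-use contacts: day 28 and day 90 (section 11.1, Table 1).
- Last EQ-5D-5L measurement: day 90 after randomisation (section 18.2.1, item 3 ii).
- Length of stay L: not given in the protocol, so assumed over a range. Randomisation is taken as the day of arrival in the ED.

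**The plan's own figure.** The costing sample is 30 × 2 × 10 = 600, which reproduces.

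**Formulas.** On the randomisation clock the cost window ends on day L + 28. The gap to day 90 is 90 − (L + 28) = 62 − L. The window as a share of the 90-day horizon is (L + 28)/90.

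| Assumed stay L (days) | Cost window ends on day | Days short of day 90 | Share of 90 days |
|---|---|---|---|
| 0 | 28 | 62 | 31% |
| 3 | 31 | 59 | 34% |
| 7 | 35 | 55 | 39% |
| 14 | 42 | 48 | 47% |
| 28 | 56 | 34 | 62% |
| 62 | 90 | 0 | 100% |
| 75 | 103 | −13 (runs past day 90) | 114% |

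The window meets the day-28 contact only for discharge on day 0, and the day-90 contact only for L = 62. For any stay between those it closes between the two contacts.

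**Between arms.** With mean stays L₁ and L₀, the difference in mean costed period is (L₁ + 28) − (L₀ + 28) = L₁ − L₀. Each day of difference in mean stay therefore moves the costed period by one day. With assumed mean stays of 6 and 7 days, the arms are costed over 34 and 35 days, a difference of 1/35, or about 3% of the longer window. The protocol gives no unit costs or readmission rates, so this cannot be turned into pounds.

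**Which cost enters the cost per QALY.** Item 1) gives a window but is not named as the input to the cost-utility analysis. Item 2) names the intervention cost as the input to the cost-effectiveness and cost-benefit analyses, and item 3 ii) sets the incremental cost of intervention against QALYs. Neither gives a period. The cost-utility analysis thus has a stated horizon for effects (day 90) and none for costs.

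**The case against.** The strongest reply is that the discharge-based window belongs to one analysis and is reasonable there. Item 1) multiplies a unit cost by incidence, using a sample drawn by care setting. That is a burden estimate, and an episode ending 28 days after discharge is a legitimate definition for it. Resource use and EQ-5D-5L are collected on the same follow-up days, so costs to day 90 can be built from what is planned. Further detail may also sit in the SAP, which was not available for this review.

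Much of this stands. A discharge-based episode is acceptable for a burden figure, and the data collection is sound. But section 18.2 asks for cost of illness by arm, and the methods give no other window for that comparison. This is a stated rule rather than an omitted detail. Section 18.2 also refers to no separate health economics plan.

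A reader might go further and infer that the cost per QALY sets costs to 28 days after discharge against QALYs to day 90, so that late readmissions reduce QALYs without adding cost and the ratio favours PCT. The documents do not support that. Items 2) and 3 ii) assign a different cost to the analysis, and the decision-tree paragraph (item 3 iii) speaks of costing all resource use, complications included. The direction is not settled either: if later treatment lengthened stays, the PCT arm would be costed over a longer window, which would count against it. What remains is that the text does not rule the carry-over out. The societal perspective is defined only in item 1), beside the discharge-based window, and the cost set against QALYs has no window of its own.

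**Conclusion.** The point holds for the per-arm cost of illness. The only patient-level cost window stated in section 18.2.1 is length of stay plus 28 days. It depends on an outcome the intervention may change, and it can give the arms unequal costed periods, one day for each day of difference in mean stay. It coincides with a scheduled resource-use contact only for a same-day discharge or a 62-day stay.

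The table rests on assumed lengths of stay and describes the window, not an error in pounds. Nothing here shows that the planned cost per QALY is biased. Its cost horizon is unstated, so any effect on it is conditional on the item 1) cost being used, and the direction is unknown. The co-primary clinical analyses are not affected. The change is worth making because the rule as written makes an arm comparison unequal and can be corrected by wording alone.

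**What to change.** 1. In section 18.2.1, item 1), replace the discharge-based window for the by-arm costs with randomisation to day 90, or to death if earlier, for both perspectives. Use the day-28 and day-90 resource-use data already scheduled.
2. In items 2) and 3 ii), state that the costs set against QALYs run over the same period, and say whether cost-of-illness costs enter that comparison.
3. Apply the exception for patients recruited in the last three months to costs and QALYs alike.
4. If a discharge-based episode cost is wanted for the national burden estimate, keep it for that purpose only and label it as such.

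The cost is protocol wording and slightly more costing work. No new data collection is needed.

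### The cost-of-illness mean rests on equal quotas of ward and ICU patients, with no ED-discharge group and no stated weighting, so it does not represent the randomised population whose cost by arm is promised

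*Protocol*

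**What the plan says.** Protocol Section 18.2 lists as its first economic output the "Cost of illness per patient from sepsis in intervention arm" and in the standard care arm, from the NHS and household perspectives. Of the economic analyses as a whole it says: "They will follow the intention-to-treat of the primary clinical effectiveness and safety analyses".

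Section 18.2.1, part 1 (cost of illness), then fixes the sample: "30 patients of each type (general ward and ICU), of 10 hospitals will be included to calculate the mean costs of illness", which it totals as 600. It describes the scaling twice. Total cost comes from "multiplying the total incidences of sepsis with the unit cost of caring for a patient throughout an episode", and later: "By multiplying mean cost with incidence rates, the total costs will be estimated". Screening cost is added as a separate total. The part states no allocation of the 600 between arms, no group for patients who leave from the ED, and no weights for the ward and ICU groups.

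Three other places bear on this:
- Section 5.4 lists ICU admission, ICU stay, hospital stay and health resource usage as secondary outcomes.
- Section 8.1 requires only age 16 or over and ED presentation with suspected sepsis; admission is not a condition.
- Section 11.1, Table 1, records ICU use, discharge and readmissions from the notes of recruited participants, and "Direct medical costs and resource use" from patients at days 28 and 90.

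**The concern.** The promised quantity is a mean over everyone randomised to an arm. The sample is instead selected on where patients ended up after randomisation. Three consequences follow from the text.

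- Half of the sample is ICU patients by construction, whatever the trial's real ICU share.
- Level of care is something the intervention may change. Selecting on it departs from intention to treat, and any comparison of arms inside the sample inherits that selection.
- Patients discharged from the ED contribute nothing to the mean, although fewer hospitalisations are among the savings that Section 18.2 anticipates.

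At stake is the cost-of-illness figure for each arm, and any later calculation that borrows it. The co-primary analyses are untouched.

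**Working it through.** **The plan's own figure.** 30 patients × 2 types × 10 hospitals = 600, which agrees with Section 18.2.1. Of these, 300/600 = 50% are ICU patients and 0% are ED discharges. The sample is 600/7676 = 7.8% of the planned trial size.

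**Inputs not in the protocol.** It gives no ICU share, no ED-discharge share and no relative costs. Everything below rests on assumed values, with ward cost set to 1.

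**1. Size of the distortion in an unweighted mean.** Let p be the ICU share among admitted patients and k the ICU:ward cost ratio.

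- Quota mean = 0.5k + 0.5
- True mean among admitted = pk + (1 − p)
- Ratio = (0.5k + 0.5) / (pk + 1 − p)

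| p | k | Quota mean | True mean | Ratio |
|---|---|---|---|---|
| 0.15 | 3 | 2.0 | 1.30 | 1.54 |
| 0.10 | 5 | 3.0 | 1.40 | 2.14 |
| 0.05 | 8 | 4.5 | 1.35 | 3.33 |

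For p below 0.5 the ratio rises with k and falls with p, so the first and last rows bound the range p = 5-15%, k = 3-8.

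**2. Comparing arms inside the quota sample.** The quotas are per hospital and type, not per arm. Assume equal numbers admitted in each arm, ICU rates of 8% (PCT) and 10% (control), and representative sampling within each type.

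- ICU patients: 300 × 8/18 = 133 PCT and 300 × 10/18 = 167 control
- Ward patients: 300 × 92/182 = 152 PCT and 300 × 90/182 = 148 control
- ICU share in the sample: 133/285 = 47% PCT and 167/315 = 53% control

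A true gap of 2 percentage points appears as about 6. With k = 5 the true difference in mean cost is (1 + 4 × 0.08) − (1 + 4 × 0.10) = −0.08. In the sample it is (1 + 4 × 0.468) − (1 + 4 × 0.529) = −0.24. The difference does not vanish, but it is not the right one.

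**3. Why ward/ICU weights alone would not suffice.** Assume ED discharge in 30% (control) and 40% (PCT), ICU in 10% of each arm, ICU cost 5 and ED-only cost 0.1.

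- All patients, control: 0.3 × 0.1 + 0.1 × 5 + 0.6 × 1 = 1.13
- All patients, PCT: 0.4 × 0.1 + 0.1 × 5 + 0.5 × 1 = 1.04
- True difference: −0.09 (−0.07 if an ED-only episode costs 0.3)
- Admitted patients only: (0.5 + 0.6)/0.7 = 1.571 control and (0.5 + 0.5)/0.6 = 1.667 PCT, a difference of +0.095

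Even with correct ward/ICU weights, leaving out ED discharges can reverse the sign.

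**The case against.** The best defence is that this is ordinary stratified sampling for unit costs. Equal quotas are a sensible way to get a stable ICU cost when ICU patients are few. The reference to patients of each type and to incidence rates can be read as type-specific means scaled by type-specific rates, with the weighting left to an analysis plan that is not shown. This stands in part: on that reading the overstatement in step 1 does not arise. But the section itself specifies the sample, its two groups and the scaling, and it mentions no weights. No weighting can recover ED-only patients, because the sample contains none.

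Two stronger readings are tempting, and the protocol does not support them.

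- A reader might infer that the quotas force both arms to the same ICU share, so that an effect on ICU use contributes exactly nothing. No quota per arm is stated. As step 2 shows, the difference would be distorted, not erased.
- A reader might infer that savings from avoided admissions cannot appear anywhere in the economic evaluation. Parts 2 to 4 of Section 18.2.1 draw on antibiotic use compared between arms, inputs quantified by arm, reduced admissions, resource use including complications, and hospital days. Nothing confines those parts to the 600.

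It is also fair that Section 18.2 states the first output as a cost in each arm and leaves the between-arm increments to its later items. Screening cost is added separately, so the cost of ED-only patients is missing from the mean but not wholly from the total.

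**Conclusion.** The point holds as an inconsistency between the promised quantity and the sample fixed to estimate it. A sample with equal numbers of ward and ICU patients, no ED discharges and no stated weights does not give a per-patient cost by arm on intention to treat.

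Its size depends on how the mean is formed. Unweighted, it is about 1.5 to 3.3 times the true mean among admitted patients, under the assumed 5-15% ICU share and cost ratio of 3-8. With suitable ward/ICU weights that overstatement goes, but the omission of ED-discharged patients remains. The damage is limited to the cost-of-illness estimate and whatever reuses it. It does not by itself invalidate the cost-saving, cost-effectiveness or cost-benefit parts. It should be corrected because the better method uses data the trial already collects.

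**What to change.** Rewrite the sampling paragraph of Section 18.2.1, part 1, to say that:

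- cost of illness per patient is computed by arm over all randomised patients, including those discharged from the ED, from the ICU use, length of stay, discharge and resource-use data already collected (Section 5.4; Section 11.1, Table 1);
- the 600-patient sample serves only to estimate ward and ICU unit costs, and household costs by type, which are then applied to each arm's observed counts;
- ED-only patients are costed from the resource use the trial records for them, since reweighting the 600 cannot represent a group with no members.

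Patients recruited in the last three months are exempt from the day 28 and day 90 questionnaires (Section 11.1). The paragraph should say that their patient-reported costs fall under the imputation of missing economic data already foreseen in Section 18.2.

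The cost is one revised paragraph and some extra analysis work, with no new data collection.

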16.2 Sample size

The sample size calculation is based on two co-primary outcomes [36] :

1. 28-day mortality, for which we want to show non-inferiority of the PCT guided assessment as compared to current standard practice, using an absolute 2.5% non-inferiority margin. Assuming a 28-day mortality of 15% in patients managed as suspected sepsis treated in the ED [3, 12], this means that any increase in 28-day mortality from 15% to not more than 17.5% would be considered non-inferior. For

90% power and one-sided 5% significance level the sample size required is 7002, assuming there is no difference in 28-day mortality between arms. Our patient focus group were also consulted on the 2.5% non-inferiority margin and felt that this was acceptable if there were mechanisms to monitor trial outcomes, and if this was what was needed to provide a sample size which would ensure the trial could be completed as well as answer the research question.

2. Initiation of antibiotics treatment, for which we want to show superiority. Currently around 90% of patients managed as suspected sepsis receive antibiotics (RLBUHT, unpublished data). A reduction by 10 percentage points to 80% would be considered a success. To detect such an effect with 90% power and two-sided 5% significance level the sample size required is 532, which is substantially lower than what is needed for the non-inferiority endpoint. With 7002 patients we would be able to detect effects as small as a reduction from 90% to 87.6% prescriptions, with 90% power.

Accounting for 5% dropout, we need a total sample size of 7372. We include one interim analysis (after 50% of patients have provided data) with options to stop the trial early using group-sequential O'Brien-Fleming boundaries [37, 38]. We will consider stopping for effectiveness if:

- the PCT guided assessment is superior in terms of 28-day mortality (i.e. a significant reduction to less than 15%), or
- the PCT guided assessment is non-inferior in terms of 28-day mortality and superior in terms of initiation of antibiotics.

We will consider stopping for futility if the results of the interim analysis suggest futility for both endpoints.

The group-sequential design will increase the total maximum sample size (if the study is not stopped after the interim analysis) by just over 4% to 7676 (inflated for 5% dropout). However, the sample size will be substantially smaller if the trial does get stopped early.

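### The initial cost-effectiveness rule treats non-inferior mortality as no difference and picks the cheaper arm, so that one step gives no weight to deaths within the margin

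*Protocol*

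**What the plan says.** Section 18.2.1, item 3 i) rests the cost-effectiveness analysis on the assumption that 28-day mortality in the two arms "is non-inferior (no significant difference"). It infers that the analysis starts as a cost-consequence or minimisation analysis in which "only the costs of interventions (IA and SCA) need to be compared to find the cost-effective alternative". The care with lower intervention costs, per patient screened and per sepsis patient treated, "will be considered as the more cost-effective alternative".

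Section 16.2 defines non-inferiority on mortality "using an absolute 2.5% non-inferiority margin", and spells this out: "any increase in 28-day mortality from 15% to not more than 17.5% would be considered non-inferior".

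Two other parts of section 18.2 bear on the point. The list of economic analyses sets the cost-effectiveness analysis in terms of life years saved and QALYs gained. After the cost-only step, section 18.2.1, item 3 ii) adds a cost-utility analysis: "Health outcomes (QALYs) between IA and SCA will be compared with incremental costs of intervention between the arms", plotted on a cost-effectiveness plane. Item 3 iii) adds a probabilistic decision tree that also uses QALYs. No sentence ranks these three parts.

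**The concern.** Non-inferiority shows that an increase in deaths is probably smaller than the margin. It does not show that mortality is equal, and it is not the same finding as a non-significant test of difference. Cost minimisation is justified only when outcomes can be taken as equal. Item 3 i) gets there by equating the two terms and then names a winner on cost alone.

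Two consequences follow within that step. If the PCT arm were cheaper and had more deaths inside the margin, it would be called the more cost-effective arm with no weight on those deaths. And because of the parenthesis, a result that is merely non-significant, and in fact fails non-inferiority, could be taken to satisfy the assumption. A cost-only comparison also cannot give the cost per life year or per QALY that section 18.2 promises.

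**Working it through.** **Inputs.** From section 16.2: control mortality 15% ("Assuming a 28-day mortality of 15% in patients managed as suspected sepsis"), margin 2.5 points, one-sided 5% level, 90% power, no true difference, 7002 evaluable, and a maximum of 7676 including 5% dropout. Allocation is 1:1 (section 6.1).

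**1. Reproduce the plan's figure.** Per arm n = (1.645 + 1.282)² × 2 × 0.15 × 0.85 / 0.025² = 3495 after rounding up. The total is 6990, within 0.2% of the stated 7002. A one-sided 2.5% level would give 8576, so one-sided 5% is the level in use.

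**2. Standard error.** With 7002 / 2 = 3501 per arm and 15% in both arms, SE = √(2 × 0.15 × 0.85 / 3501) = 0.853 points. At the maximum size, 7676 × 0.95 / 2 gives about 3646 per arm and SE = 0.836 points.

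**3. Where each label stops applying.** Let d be the observed excess in the PCT arm and SE(d) the unpooled standard error with 15% in the control arm.

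- Non-inferior: d + 1.645 × SE(d) < 2.5 points.
- Not significant: d < 1.96 × SE(d). Section 18.2.1 gives no level for this term, so two-sided 5% is my assumption. One-sided 5% is shown as well.

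| Per arm | Largest d that is non-inferior | Largest d not significant, two-sided 5% | Same, one-sided 5% |
|---|---|---|---|
| 3501 | 1.08 points | 1.71 points | 1.43 points |
| 3646 | 1.10 points | 1.68 points | 1.40 points |

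At 3501 per arm, 1.076 points is about 38 extra deaths in the PCT arm (0.01076 × 3501). An observed excess between about 1.1 and 1.7 points is non-significant but not non-inferior. Allowing for the interim look with a critical value of 1.678 gives 2.5 − 1.678 × 0.836 = 1.10 points, so the limit barely moves.

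**4. How often this arises (3501 per arm).**

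| True excess | Probability of declaring non-inferiority | Probability of a non-significant result, two-sided 5% |
|---|---|---|
| 0 | 0.90 | 0.95 |
| 1.0 point | 0.54 | 0.79 |
| 2.5 points | 0.05 | 0.19 |

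**5. What item 3 i) leaves out, in money.** The protocol gives no QALY loss per death, no threshold and no time horizon. Assume £20,000-30,000 per QALY and a 1-point excess (0.01 deaths per patient).

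- 90-day horizon, the last EQ-5D-5L time point: a death loses at most about 90/365 ≈ 0.25 QALY. Then 0.01 × 0.25 = 0.0025 QALY per patient, or £50-75.
- Long horizon, assuming 2-10 QALYs lost per death: 0.01 × 2 = 0.02 to 0.01 × 10 = 0.10 QALY per patient, or £400 (0.02 × £20,000) to £3,000 (0.10 × £30,000).

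The two cases differ widely, so no single figure should be quoted as the size of the problem.

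**The case against.** The strongest reply is that the protocol does not stop at the cost comparison. It is described as a first step, which gives an order and not a precedence. The cost-utility analysis and the decision tree both count QALYs, and the protocol itself commends the cost-effectiveness plane for decisions in non-inferiority trials. The mixed label for item 3 i), which joins cost-consequence with minimisation, suggests loose drafting more than a firm intention to ignore deaths.

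Most of this stands. A reader might infer that the economic evaluation as a whole ignores mortality, or that the trial's cost-effectiveness conclusion could have the wrong sign. The documents do not support that, because it would require item 3 i) to override items ii) and iii), and nothing says that it does. A reader might also infer that better survival at a slightly higher cost would be rejected. That too goes too far: a significant survival gain breaks the stated assumption, section 5.3 classes decreased mortality as effective, and a non-significant gain is unweighted only in item 3 i).

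A 1-point excess is also near the limit of what passes. If there were no true difference, an observed excess between 1.0 and 1.1 points would occur with probability of about 2% at the maximum size.

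The reply does not rescue the text of item 3 i). The gloss is wrong as written, and a rule that names the more cost-effective arm on cost alone stands beside analyses that can contradict it.

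**Conclusion.** The point holds for item 3 i) only. Its gloss on non-inferiority conflicts with section 16.2, and its lower-cost rule gives no weight to any mortality difference that meets the assumption: up to about 1.1 points observed if non-inferiority is the test, or about 1.7 points if non-significance is. These limits assume 15% control mortality and the planned size. They would shift if the arcsine frontier in section 17.1 replaced the fixed margin.

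The conclusion of item 3 i) could therefore have the wrong sign if the cheaper arm had more deaths. The QALY-based parts soften this without removing it, because no order of precedence is given. A reader might take a figure above £1,000 per patient as the stake, but that needs a long horizon that the protocol does not state. On the 90-day measurements alone the value is £50-75 per 1-point excess, at thresholds that are themselves assumed.

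Cost-effectiveness is a secondary objective. The co-primary analysis and the effectiveness decision in section 5.3 are not affected.

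**What to change.** In section 18.2.1, item 3 i), delete the parenthesis that equates non-inferiority with no significant difference, and delete the rule that the lower-cost arm is the more cost-effective one. State that the planned cost-utility analysis is the basis for the cost-effectiveness conclusion whatever the non-inferiority result, with joint uncertainty in incremental cost and QALYs shown on the cost-effectiveness plane. Keep the cost-only comparison as a descriptive result.

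This is a change of wording. It needs no new data and no new analysis, since the cost-utility analysis is already planned. If QALY losses beyond day 90 are meant to count, that analysis would also need a stated horizon and an extrapolation method, which is more than a wording change.
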